### Power Calculation:

We conservatively estimate an 8% difference in effect size (i.e., >5% weight loss) comparing intervention and control group participants. Accrual of 1040 participants, evenly randomized to intervention or control groups, provide greater than 80% power to detect this difference, using a 2-sided, 0.05-level test (i.e., 52 participants (26 Intervention and 26 control participants per PCP). These calculations assume 15% loss to follow-up and enrollment of 20 PCP sites.

**Sampling:** Preliminary data from our practice needs assessment indicates that approximately 444 unique patients for every six months will have an office visit. Based on population estimates, we estimate that 29% of those individuals will be ineligible due to a pre-study period T2DM or pre-diabetes diagnosis (n=129) and approximately 69% of remaining patients will have a BMI  $\geq 23$  kg/m^2, making them eligible for the study (n=217). In our ongoing T2DM management CHW intervention among South Asians, screening to enrollment rate is 41%. For this study, we apply a conservative estimate that 30% of patients will consent to be contacted by a CHW and receive an HbA1c test (n=65). Based on populations estimate, we anticipate that 43% of those individuals will have pre-diabetes (n=28). Based on retention rates from our CHW studies, we conservatively estimate that approximately 85% of individuals assigned to a CHW will be followed up at six months (n=24). Thus, for each PCP, we will enroll approximately 24 patients every six months over a period of one year, resulting in total recruitment of 960 across 20 PCPs. This equates to an approximate CHW caseload of 13 patients per month for a part-time CHW, consistent with caseloads from our previous studies.

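### Enrolment is set at 1040 in some places and 960 in others, and the 960 comes from a count taken after follow-up losses

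*Combined protocol and SAP*

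**What the plan says.** Three places set enrolment at 1040:

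- Section I.A (Purpose of the Study) gives 1040 patients in 20 PCPs.
- Section II (Characteristics of the Research Population) gives 1040 within an overall total of 1220.
- Section III.B1, Power Calculation, says "Accrual of 1040 participants, evenly randomized to intervention or control groups, provide greater than 80% power to detect this difference" and breaks this down as "52 participants (26 Intervention and 26 control participants per PCP". It adds: "These calculations assume 15% loss to follow-up and enrollment of 20 PCP sites". This is the only place that gives 52 per PCP.

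Two places set it at 960:

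- Figure 1 (Section I.C1) schedules 48 patients to be recruited and enrolled at every PCP and expresses each wave as a share of a 960-patient target.
- The Sampling paragraph, directly below the power statement, says "we will enroll approximately 24 patients every six months over a period of one year, resulting in total recruitment of 960 across 20 PCPs". It does not state 48 per PCP, but 24 in each of two six-month periods gives that number.

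The 24 is the last step of a recruitment funnel. The step before it is 28 patients with pre-diabetes per PCP per six months. The final step is that "85% of individuals assigned to a CHW will be followed up at six months (n=24").

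**The concern.** A trial needs one enrolment number, with a clear statement of whether it is before or after attrition. Here two numbers, both described as enrolment or recruitment, stand in adjacent paragraphs, and nothing reconciles them. The power statement belongs to one of them (1040), while the site-level schedule in Figure 1 follows the other (960).

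The Sampling paragraph also takes a count of patients followed up at six months and, in the next sentence, calls it the number enrolled. If sites enrol that number and 15% are then lost as the Power Calculation assumes, the same attrition is taken off twice.

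At stake are how many patients are available for the primary comparison (5% or more weight loss at six months) and whether the power statement describes the trial that Figure 1 would deliver.

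**Working it through.** **Step 1. Reproduce the 960.** All inputs are from the Sampling paragraph, per PCP per six months, with the plan's own rounding.

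- Patients with an office visit: 444
- Prior diagnosis: 444 × 0.29 = 128.8, so 129 excluded and 315 left
- BMI eligible: 315 × 0.69 = 217.4, so 217
- Consent to contact and HbA1c test: 217 × 0.30 = 65.1, so 65
- Pre-diabetes: 65 × 0.43 = 27.95, so 28
- Followed up at six months: 28 × 0.85 = 23.8, so 24
- Two periods, 20 PCPs: 24 × 2 × 20 = 960

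The plan's figure reproduces. Figure 1 agrees with it: 7 × 48 = 336, 6 × 48 = 288 and 7 × 48 = 336, which sum to 960. (The wave 3 entry reads 36 in the text available; the stated 35% and 7 × 48 both indicate 336.)

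**Step 2. Reproduce the 1040.** 52 × 20 = 1040, and 1040 + 80 + 100 = 1220, as in Section II.

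**Step 3. Is 960 the evaluable part of 1040?** No. 1040 × 0.85 = 884. Working back from the rounded figure, 960 / 0.85 ≈ 1129. The 15% loss does not connect the two numbers.

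**Step 4. What does the funnel give before attrition?** 28 × 2 × 20 = 1120 enrolled (56 per PCP), of whom 1120 × 0.85 = 952 would be followed up. The 8 patients between 952 and 960 come from rounding 23.8 up to 24. So 960 is in effect the followed-up count of an enrolment of about 1120, and 1120 is neither stated target.

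**Step 5. Size of the gap.** 1040 − 960 = 80 patients, and 80 / 1040 = 7.7%. After 15% loss, 1040 leaves 884 (442 per arm) and 960 leaves 960 × 0.85 = 816 (408 per arm).

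**Step 6. Effect on power.** The Power Calculation gives a two-sided 0.05 test and "We conservatively estimate an 8% difference in effect size". It gives no control rate and does not say whether 8% is absolute. I take it as 8 percentage points and try a range of control rates p₀, with p₁ = p₀ + 0.08, p̄ = (p₀ + p₁)/2 and n per arm:

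power = Φ{ [0.08√n − 1.96√(2p̄(1 − p̄))] / √(p₀(1 − p₀) + p₁(1 − p₁)) }

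Worked case, p₀ = 0.10, n = 442: 0.08√442 = 1.682; 1.96√(2 × 0.14 × 0.86) = 0.962; √(0.09 + 0.1476) = 0.487; (1.682 − 0.962)/0.487 ≈ 1.48; power ≈ 93.0%.

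| Assumed control rate | 442 per arm (1040 enrolled) | 408 per arm (960 enrolled) | Difference (points) |
|---|---|---|---|
| 5% | 98.7% | 98.0% | 0.7 |
| 10% | 93.0% | 91.0% | 2.0 |
| 15% | 85.9% | 83.1% | 2.8 |
| 20% | 79.6% | 76.4% | 3.2 |
| 25% | 74.7% | 71.2% | 3.4 |
| 30% | 71.0% | 67.5% | 3.5 |

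(Differences are taken before rounding.) Power of 80% is reached up to a control rate of about 20% with 442 per arm and about 17% with 408.

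**The case against.** The best defence is that the two numbers do different jobs. The 1040 is the design number: it is tied to the power claim and to equal individual randomisation, and it fits the 1220 total. The Sampling paragraph would then be only a feasibility estimate. With 28 read as the number enrolled, the funnel projects about 1120 available, more than the 1040 needed, and so supports the design. This has force. It rules out the inference that the funnel shows 1040 to be unreachable. It does not remove the contradiction, because Sampling and Figure 1 both present 960 as the number to be enrolled. The 1120 is also only the funnel's own arithmetic: its consent step ("30% of patients will consent to be contacted by a CHW and receive an HbA1c test (n=65") and its retention step are worded for patients offered a community health worker, and the plan does not say how they apply to controls, who contribute health-record data under a waiver.

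A second defence is that the 960 may be left over from the stepped-wedge plan that Section I.C1 mentions. That is possible but unproven, and Section I.A pairs 1040 with stepped-wedge wording.

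A third is that the consequence is small. That stands. A reader might infer that the trial is underpowered or that the power claim is wrong. The documents do not support this: with no control rate stated, the claim can be neither confirmed nor refuted, and at control rates up to about 17% both targets exceed 80%. The choice of target decides the matter only between about 17% and 20%. If no one were lost, as the Aim 1 analysis text expects, the gap between 1040 and 960 would be smaller still: 1.4, 2.3 and 2.9 points at control rates of 10%, 15% and 20%.

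Finally, the protocol version is dated 9.28.21 and Figure 1's calendar runs from April 2018 to March 2022, so much recruitment may already have taken place. Raising Figure 1 to 52 is therefore not automatically a mere text change. The fix allows for this.

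**Conclusion.** The point holds as an inconsistency in the enrolment target together with an error in how attrition is counted. The plan states both 1040 and 960 as enrolment for the same 20 PCPs. The 960 is a followed-up count labelled as enrolment, and the matching pre-attrition count, 1120, is neither target. Only 1040 carries the power claim.

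If sites work to Figure 1, the trial enrols 80 fewer patients and, after 15% loss, has 816 evaluable instead of 884. The cost is modest: 0.7 to 3.5 points of power over control rates of 5% to 30%. No test or error rate changes, and the power claim is not shown to be false.

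The enrolment arithmetic rests only on the plan's numbers. The power figures rest on three assumptions of this review: that 8% is an absolute difference, the range of control rates, and a simple two-proportion test in place of the planned mixed model. Matching, group delivery and the quarter effects are not modelled.

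**What to change.** State one enrolment target throughout, say that it is before attrition, and apply the 15% loss once.

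- **If 1040 is kept:** change Figure 1 to 52 per PCP, with waves of 364, 312 and 364 (7 × 52, 6 × 52, 7 × 52; total 1040). In Sampling, label 28 as enrolled and 24 as followed up, and replace the 960 recruitment total with a statement that the funnel projects about 1120 available against the 1040 needed. Sections I.A and II stay as they are.
- **If 960 enrolled is the working target:** change 1040 to 960 in Section I.A, Section II and the Power Calculation; change 52 (26 + 26) to 48 (24 + 24); change 1220 to 1140 (960 + 80 + 100). Correct the Sampling derivation so that 24 enrolled is not a post-attrition count. Restate power at 816 evaluable (408 per arm), giving the control rate used.

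The cost is text corrections only if sites are already recruiting to the target that is kept. If they have been recruiting to 48 per PCP, choose 960 and restate the power. The stated power then becomes slightly less favourable, but no additional enrolment is needed.

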### B2. Aim 2 Analysis.

Analysis to address this aim will be guided by the following questions:

**1. Utilization Patterns:** How frequently do clinicians utilize the integrated EHR-CHW system? What is the percentage of adoption? Does the utilization pattern change over time? Does the intervention increase the utilization and quality of quality measurement reports?

The system utilization files from HF's data warehouse will be used to analyze utilization patterns of the enhanced physician alert and registry functions, as well as the integrated EHR-CHW options. These data will yield descriptive trends for frequency of utilization across the participating PCPs as well as an estimate of the percentage of adoption in terms of patient visits for HbA1c screening. The frequency of quality measurement reports will be described and compared 12 months pre- and post- intervention.

**2. Physicians' Attitudes Regarding the Integrated Intervention:** What are physicians' attitudes regarding ADA recommendation for testing of pre-diabetes at BMI  $\geq 23$  kg/m^2? How satisfied are the physician's with the integrated EHR-CHW tools? What are the barriers and facilitators of point-of-care use of the tools? How does the intervention affect clinicians' satisfaction with workflow around T2DM prevention and weight loss?

This set of research questions will be primarily addressed with data from brief surveys collected from the participating clinicians. Survey items with response scales will be designed to capture data on each of the research questions above. For instance, participants may be asked to respond on a five-point scale from strongly agree to strongly disagree to the following statements: "Pre-diabetes testing recommendations are useful to me in my practice", or "The HbA1c testing alerts in the EHR are helpful to me", or to indicate how frequently they use each in a set of common information sources for clinical decision support. The survey data come from a small sample (n=approximately 40) and are only intended to quantify descriptive information and will not be used in extensive statistical analyses. The data will be tabulated and summarized descriptively to address each research question listed above and to assess change in attitudes from baseline to 12 months.

**3. Barriers and Facilitators to Implementation Adoption and Implications for Scalability:** What organizational barriers and facilitators appear to influence implementation and how? Did members of the practice understand and respect the respective roles of physicians, CHWs, and other members of the team? How did this organization customize the intervention to better serve its own local needs? How were users involved in design and implementation? What are recommendations for replicating this model for other clinical settings and communities? Do project findings motivate payer organizations to reimburse CHW services?

Interview data will be transcribed and analysis transcribed data will follow "constant comparison" analytic approach. The "constant comparison" approach is a method of explanation building in which the findings of an initial case are compared to a provisional category, property or proposition, revised as necessary and then other details or new cases are then compared against the revision and revised again as needed. This process is continued until an area of interest is fully explicated, reaching theoretical saturation. Using "thematic" coding, we will develop an initial set of codes, which will be reviewed by the community-clinical coalition to ensure they are relevant and complete. For each core code, we will ultimately develop one or more "secondary codes" that represent either more specific or restricted aspects of the phenomenon, to contextualize it, or to suggest underlying meanings. The secondary codes will vary in specificity or subtlety depending on the judged substantive value of additional refinements. Transcripts will be coded by at least four coders. Discrepancies in coding will be discussed and resolved, then the process is repeated with a new set of transcripts until an acceptable level of inter-coder reliability between them has been achieved, estimated using an appropriate chance-corrected statistic (e.g., kappa for nominal data and T-index for ordinal data). The coded transcripts will be analyzed with *Atlas.ti*, a software package for qualitative data analysis. Analysis will be conducted to inform best practices for scalability that can be replicated by payer organizations and health care systems.

**4. Cost-Effectiveness/Sustainability:** What were the costs of the integrated intervention to the insurer organizations and physician practice and did these additional costs provide added value at patient and provider levels? What were the net costs and benefits of different combinations of CHW and EHR interventions?

Using average resource utilization and costs per patient (in first 6 and 12 months of follow-up), we will compare resources incurred by the trial arms during the follow-up period at each time point. Our outcome will be the incremental cost per person achieving 5% weight loss. Cost data will be used to inform HF leadership of program costs for consideration of sustainability of CHW models by payer organizations.

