## C. Study Design

### C1. Overall Design/Site Selection/Site Enrollment

We will use a randomized controlled trial design with staggered-entry and a waitlist controlled group to compare the effectiveness of an alert and registry-driven CHW-led coaching compared with usual care among patients with BMI at baseline of  $\geq 23 \text{ kg/m}^2$ . Randomization will be at the individual-level and stratified by PCP, meaning eligible intervention and control participants will be randomized for each PCP. PCPs will be clustered into waves, aligning with the original stepped-wedge design. Entry into the study will be staggered in three waves, with each wave consisting of six to seven PCPs (See Figure 1). All 20 PCPs will be recruited and enrolled by month 6 of Year 2 (study period 6, Figure 1), and we will assign 6-7 practices into each of the 3 waves upon enrollment. For each PCP, there will be a total of two rounds of consecutive six-month CHW intervention periods: 1 month for recruitment and enrollment of intervention participants and five months of community health worker-led group education sessions (approximately one session per month). Data related to the study outcomes will be extracted from EHR systems a total three times (baseline, 6 month, and 12 month) for each PCP. Randomization at each PCP will occur during the first round. Prior to allocation into treatment group, each treatment participant will be matched to a control participant based on age, gender, and BMI. Intervention participants will be split into two groups and assigned to either first or second round. All control participants will be waitlisted during the first round and will be offered the full CHW group education sessions during the second round. PCPs will be placed into waves based on geographic location and CHW caseload considerations. PCPs will be eligible for participation if they have a) an overall patient volume of  $N \geq 1000$ ; b) at least 70% of the patient population is South Asian; and c) the practice has used EHR for at least 12 months. All PCPs will sign a Memorandum of Understanding (MOU) between the PCP and NYU outlining study commitments.

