#### C4. Provider Survey

At baseline and follow-up, brief surveys will be administered to all participating physicians (n=80) by the NYU study team to capture data on: satisfaction with workflow before and after intervention, information

sources for EHR-CHW initiatives before and after intervention, acceptability of and satisfaction with the integrated EHR-CHW intervention, and barriers and facilitators of point-of-care use of the tools (See *Provider Survey and Provider Survey – Follow-up*). The follow up provider survey will also include additional variables of organizational climate and priority and effects of the COVID-19 pandemic at the individual practices (eg. including questions to assess impact of COVID-19 on the practice and if providers are providing and/or tracking COVID-19 vaccination among patients in order to inform tailoring of remote intervention to support vaccination efforts and assist follow-up by CHWs to encourage vaccination among patients with overweight and pre-diabetes who are at higher risk for complications from COVID-19)

Survey items with response scales will be designed to capture data on each of the research questions. For instance, participants may be asked to respond on a five-point scale from strongly agree to strongly disagree to the following statements: “Pre-diabetes testing recommendations are useful to me in my practice”, or “The HbA1c testing alerts in the EHR are helpful to me”, or to indicate how frequently they use each in a set of common information sources for clinical decision support. Provider Surveys will be administered via online survey software or paper copy if requested. Surveys will take approximately 15 minutes to complete.

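### Aim 2 asks whether the intervention increases use of quality measurement reports, but the planned 12-month before-after comparison cannot separate that from calendar change

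*Combined protocol and SAP*

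**What the plan says.** Section III.B2, item 1, poses the question "Does the intervention increase the utilization and quality of quality measurement reports". The answering analysis is one sentence: "The frequency of quality measurement reports will be described and compared 12 months pre- and post- intervention". For the alert, registry and EHR-CHW functions the same paragraph offers description: "These data will yield descriptive trends for frequency of utilization across the participating PCPs". It names no comparator practices, model or calendar-time adjustment for the report counts.

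Three features of the design bear on this:

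- Section C1 states "Randomization will be at the individual-level and stratified by PCP", while section C2 and the list of intervention components in III.A1 put the EHR changes in place at every participating practice.
- Section C1 also states "Entry into the study will be staggered in three waves, with each wave consisting of six to seven PCPs" and "PCPs will be placed into waves based on geographic location and CHW caseload considerations". Figure 1 lists 7, 6 and 7 practices in the three waves and spans April 2018 to March 2022.
- Section C4 adds to the follow-up provider survey questions on the "effects of the COVID-19 pandemic at the individual practices", and section C5 does the same for follow-up interviews. Neither is linked to the analysis of report counts.

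The only calendar-quarter term in the plan is in the Aim 1 model for patient weight loss (III.B1).

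**The concern.** The question asks about an effect, but the comparison measures change. How often a practice runs or receives quality reports can drift for reasons unrelated to the study, such as payer reporting requirements, EHR upgrades, staffing or visit volume. An uncontrolled before-after ratio adds all of these to whatever the intervention did. The randomised arms cannot remove them, because intervention and waitlist patients of one physician sit in the same exposed practice and the outcome belongs to the practice.

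What is at stake is the answer to one Aim 2 question. A trend could be reported as uptake caused by the intervention, or a real increase could be hidden by a fall in practice activity.

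**Working it through.** The plan gives no baseline rate, effect size or precision for this comparison, so there is no stated figure to reproduce.

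**Step 1: what could serve as a control.** The patient arms cannot, for the reason above. The Aim 1 quarter effect belongs to another model and another unit of analysis. Practices in later waves could, for as long as their EHR changes are not yet live.

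**Step 2: how a trend passes through.** Assume that each practice's windows are adjacent and meet at its own start; the plan does not say so. Let the expected count in month m be b(1+g)^(m/12), multiplied by E once the intervention is live. Each post-window month lies exactly 12 months after its matching pre-window month, so

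post/pre = E × (1+g)^(12/12) = E(1+g).

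With E = 1 (no effect), g = +5%, +10%, +20% and −10% per year give ratios of 1.05, 1.10, 1.20 and 0.90.

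**Step 3: simulation with no true effect.** The practices and waves (20; 7, 6, 7) come from Figure 1. The rest is assumed: 10 reports per practice-month, between-practice log-SD 0.4, log-SD of practice-level change 0.2, waves 12 or 15 months apart, any step change 21 months after wave 1 starts, and 1,500 runs per setting. Where two values are shown, they are for the 12- and 15-month gaps.

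| Calendar pattern | Post/pre ratio | Nominal 5% test rejects |
|---|---|---|
| none | 1.00 | 6% |
| +5% per year | 1.05 | 13%, 14% |
| +10% per year | 1.10 | 42%, 41% |
| +20% per year | 1.20 | 92% |
| −10% per year | 0.90 | 42%, 41% |
| lasting 30% drop | 0.89, 0.92 | 48%, 27% |
| lasting 30% rise | 1.09, 1.07 | 31%, 19% |
| +10% per year and 30% drop | 0.98, 1.01 | 5%, 4% |

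The plan names no test, so the last column only shows how large the bias is relative to noise under these inputs. In the same runs, a contrast with not-yet-started waves over the same months gave ratios of 0.998 to 1.004 and rejected in about 4% to 6% of runs. That is partly by construction, since the simulated shock is common to all practices.

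**Step 4: hand check of the 30% drop, 12-month gap.** Wave 1's windows end before the drop, so its ratio is 1. Wave 2's post window has 3 of 12 months after it: (9 + 3 × 0.7)/12 = 0.925. Wave 3 has 0.925 in its pre window and 0.7 in its post window: 0.7/0.925 = 0.757. The geometric mean over 7, 6 and 7 practices is exp[(6 ln 0.925 + 7 ln 0.757)/20] = 0.89, as simulated.

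**Step 5: direction of a temporary disruption.** Suppose activity is 30% lower for 6 of the 12 months of one window only. That window averages (6 + 6 × 0.7)/12 = 0.85. In the post window this gives a ratio of 0.85; in the pre window it gives 1/0.85 = 1.18. The sign therefore depends on where the windows fall.

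**The case against.** The strongest reply is that this part of Aim 2 is descriptive by design. The questions guide the analysis, no hypothesis or significance level is attached, and the paragraph speaks of descriptive trends. That stands as to weight: nothing confirmatory is at risk, and the rejection rates above belong to a test that the plan does not propose. It does not remove the point, because the sentence promises a comparison and is the only answer offered to a question about an increase.

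A second reply is that the staggered waves are a weak comparator. Waves are set by geography and CHW caseload, so a disruption that differed by area would not be removed by quarter effects. Wave 3 (7 of 20 practices) has no later wave to compare with. The gap between waves could not be read from the copy of Figure 1 reviewed, and the documents do not date EHR go-live relative to wave start. All of this stands, so a reader should not infer that a ready-made control group has been overlooked. Such a group exists only if the actual dates leave unexposed quarters.

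Third, the provider survey and interviews do gather practice-level pandemic context. This helps interpretation but does not adjust the counts.

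**Conclusion.** The point holds for one item: a question about effect is answered by a comparison that supports only a statement about change. Any common calendar trend passes in full into the ratio, as (1+g) under adjacent 12-month windows. A disruption can bias it up or down. The true size cannot be given, because the documents contain no report counts, trend or go-live dates; the figures above rest on the stated assumptions.

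Two stronger readings are not supported. One is that the adoption and scalability conclusions of Aim 2 depend on this comparison. In III.B2, adoption is estimated from HbA1c screening visits, attitudes come from surveys, scalability from coded interviews and sustainability from cost, and no before-after comparison of visits or HbA1c testing is planned. The other is that the bias must be very large. That would need a disruption to fill one 12-month window and miss the other entirely, and the documents do not show such an alignment. The primary outcome is not touched. This is a cheap improvement rather than a necessary correction.

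**What to change.** In III.B2, item 1, request counts of quality measurement reports by practice and calendar quarter for all 20 practices, and record the actual EHR go-live date of each. For the quarters in which some later-wave practices are still unexposed, fit a count model with practice effects, calendar-quarter effects and a live/not-yet-live indicator based on those dates. State the assumption that practices would have followed parallel trends. Label the result quasi-experimental, because the waves are not randomised, there are only 20 practices and wave 3 has no later comparator. Keep the raw 12-month before and after figures as description, and say how the windows are anchored.

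If the go-live dates leave no unexposed quarters, say instead that the before-after result is descriptive change and not an intervention effect, and reword the question to match.

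The cost is a finer data request, probably to the warehouse utilisation files already planned for this item, and a little more analysis. The statistical price is a wider interval than the raw comparison would show.
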